5. STUDY TREATMENT

5.1. Treatment Group Assignments

There will be 2 treatment arms for the woman during pregnancy; monthly SP or monthly DP. We will use a 1:1 randomization scheme targeting 391 pregnant women in each treatment arm. A randomization list will be computer generated by a member of the project who will not be directly involved in the conduct of the study. The randomization list will include consecutive treatment numbers with corresponding random treatment assignments. Randomized codes will correspond to the 2 treatment arms using permuted variable sized blocks of 4 and 8. Sealed copies of the original randomization list and documentation of the procedure used to generate the lists will be stored in the project administrative offices in San Francisco and Kampala. Prior to the onset of the study, a set of sequentially numbered, opaque, sealed envelopes will be prepared. Each envelope will be marked on the outside with the treatment allocation number. The inside of the envelope will contain a piece of paper with the treatment allocation number and treatment group assignment along with a piece of carbon paper.

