6. SUBJECT MANAGEMENT

6.1. Subject Follow-up

Pregnant women will be scheduled to be seen in the clinic every 4 weeks during their pregnancy and then 1 and 6 weeks following delivery. In addition, pregnant women will be instructed to come to the study clinic for all their medical care and avoid the use of any outside medications. Children will be scheduled to be seen in the clinic at 1, 4, 6, and 8 weeks of age and then every 4 weeks until they reach 52 weeks of age. Parents /guardians will be instructed to bring their children to the study clinic for all medical care and avoid the use of any outside medications. The study clinic will remain open 7 days a week from 8 a.m. to 5 p.m. Pregnant women and children who are not seen on the day of their regularly scheduled visits will be visited at home and instructed to come to the clinic as soon as possible.

Each time a study participant is seen in the clinic a standardized history and physical exam will be performed including temperature, pulse, and blood pressure measurement. Patients who are febrile (tympanic temperature \geq 3 8.0°C) or report history of fever in the past 24 hours will have blood obtained by finger prick for a thick blood smear (in very young children, heel sticks may be substituted for finger pricks). If the thick blood smear is positive, the patient will be diagnosed with malaria. If the thick blood smear is negative, the patient will be managed by study physicians for a non-malarial febrile illness (Section 6.3). If the patient is afebrile and does not report a recent fever, a thick blood smear will not be obtained, except when following routine testing schedules (Section 6.5).

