6.3. Management of Non-Malaria Illnesses

Patients who are found to have illnesses other than malaria will receive standard-of-care treatment in the study clinic, according to standardized algorithms, or will be referred to the local hospital. We will avoid the routine use of non-study medications with antimalarial activity, including antifolates (with the exception of assigned chemopreventive regimens), and macrolide antibiotics, when acceptable alternatives are available. In addition, drugs with known risk of torsades de pointes or CYP3A inhibitors (Appendix J and K) will be avoided when prescribing treatment to pregnant women during the time they are taking study drugs. If the study clinician deems treatment with one of the drugs listed on Appendix J or K is required, the clinical management team will be consulted. During follow-up for non-malarial illnesses, blood smears will be done at the discretion of the study physician if the subjects are febrile (tympanic temperature \geq 38.0°C) or report history of fever in the past 24 hours. If the blood smear is positive, the patient will be diagnosed with a new episode of malaria and managed per study protocol.

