6.4. After Hours Visits

Pregnant women will be encouraged to come to Masafu General Hospital maternity ward (open 24 hours a day) and parents/guardians will be encouraged to bring their child to Masafu General Hospital pediatric inpatient ward (open 24 hours a day) when urgent care is needed outside of study clinic hours. Pregnant women or parents/guardians of children will be instructed to inform hospital personnel of their involvement in the study at the time of registration and to visit the study clinic on the following day. If a patient is diagnosed with uncomplicated malaria they will receive treatment from a hospital supply of AL and the doctors will be instructed to refer patients to our study clinic when it opens at 8 am the following day. If a patient is diagnosed with severe malaria, he/she will receive quinine or artesunate following standard treatment guidelines. Patients with non-malarial illnesses will be managed at the discretion of the hospital staff. Upon discharge, patients will receive follow-up at the study clinic as outlined above.

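### Section 6.4 does not carry the Appendix J and K drug safeguard of section 6.3 over to pregnant women treated on the ward after hours

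*Combined protocol and SAP*

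**What the plan says.** **Section 6.3 (Management of Non-Malaria Illnesses)** sets the safeguard. Patients are treated in the study clinic "or will be referred to the local hospital". While women are taking study drugs, "drugs with known risk of torsades de pointes or CYP3A inhibitors (Appendix J and K) will be avoided when prescribing treatment to pregnant women". If the study clinician judges that "one of the drugs listed on Appendix J or K is required, the clinical management team will be consulted".

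**Section 6.4 (After Hours Visits)** covers urgent need when the clinic is shut. By section 6.1, "The study clinic will remain open 7 days a week from 8 a.m. to 5 p.m". At other times pregnant women are encouraged to use the maternity ward of Masafu General Hospital. They are told to "inform hospital personnel of their involvement in the study at the time of registration and to visit the study clinic on the following day". For uncomplicated malaria the hospital uses its own supply of AL, and "the doctors will be instructed to refer patients to our study clinic when it opens at 8 am the following day". Severe malaria is treated with quinine or artesunate under standard guidelines. For everything else the rule is "Patients with non-malarial illnesses will be managed at the discretion of the hospital staff". After discharge, follow-up returns to the study clinic.

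Outside 6.3, the two lists appear only as the appendices themselves.

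**The concern.** Section 1.1 names QTc prolongation as a safety question on which more data are needed for IPTp with DP, and section 1.3 promises repeated QTc assessment in all participants. The Appendix J and K restriction is the protocol's preventive measure on prescribing for that risk. It depends on the prescriber knowing the lists and having someone to consult.

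After hours, the prescriber is a member of the hospital staff, and the text gives that person discretion with no mention of either list. Appendix J includes ondansetron, azithromycin and erythromycin; Appendix K includes fluconazole and erythromycin. A woman who may be on DP could be given one of these before the study team hears of it, and no sentence in 6.4 would have been breached. What is at stake is participant safety and, secondarily, how a QTc finding in such a woman would be interpreted.

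**Working it through.** No figure in the plan bears on this point, so the check compares the texts.

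**1. Who is bound by 6.3?** The sentence before the drug restriction describes what the study team itself will avoid. The restriction is then worded in the passive, with no named prescriber and no limit to clinic hours. The consultation step is narrower: it is triggered by the judgement of the study clinician.

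**2. What does 6.4 pass on to the ward?**

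| Situation after hours | Direction given in 6.4 |
|---|---|
| Uncomplicated malaria | AL from hospital supply; refer to study clinic next morning |
| Severe malaria | Quinine or artesunate under standard guidelines |
| Non-malarial illness | Hospital staff discretion |
| Appendix J or K drugs | Not mentioned |
| Contact with the clinical management team | Not mentioned |

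The section therefore does direct the hospital where malaria drugs are concerned. Non-malarial illness, to which the 6.3 restriction is addressed, is the category left open.

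**3. Is the gap closed elsewhere?** Appendices J and K are cited in 6.3 and then reproduced at the end of the protocol. No other section says that the ward is given them or told whom to call.

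**4. What do the remaining safeguards do, and when?**

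- The woman tells the ward that she is in the study (6.4). This identifies her as a participant; it does not tell the prescriber what to avoid.
- She attends the study clinic the next day, with follow-up there after discharge (6.4). This comes after any first dose.
- Routine visits every 4 weeks ask about outside facilities and medications (6.5). This is retrospective.
- ECGs are done at 20, 28 and 36 weeks, around study dosing (6.5). A drug given on the ward does not trigger one.
- Adverse events are assessed at each scheduled and unscheduled clinic visit (7.1.2). This detects harm or limits continued exposure.

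Each of these can shorten or reveal an exposure. None prevents the first dose.

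**5. Whom would a ward rule have to cover?** Section 5.1 describes a "1:1 randomization scheme targeting 391 pregnant women in each treatment arm", so 391 × 2 = 782 women. Treatment is double blinded (5.4), and section 6.12 treats every woman as potentially exposed to either drug. Ward staff cannot tell who is on DP, so a rule limited to that arm would not work. The 782 is the group to be covered while on study drugs (16 to 40 weeks, section 5.4), not an estimate of women at risk.

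**6. Can the exposure be sized?** That would need the number of after-hours visits for non-malarial illness and the share of those visits in which a listed drug is prescribed. The documents give neither, nor do they say which listed drugs the ward stocks or uses.

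**The case against.** The strongest reply is that 6.3 already covers the ward. Its restriction sits in the section on non-malarial illness, follows a reference to hospital referral, and is not limited by hour or prescriber. Discretion over management need not cancel a drug restriction. This is a fair reading and cannot be excluded. It does not make the safeguard work, though: a restriction by list needs the list in the prescriber's hands, and the consultation step names only the study clinician.

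A second reply is that the ward is no remote provider. The study clinic is inside the same hospital, after-hours care is part of the site arrangement in the Schema, women agree at entry to bring illnesses to the study clinic and to avoid outside medications, and follow-up is prompt. All of this stands and reduces continued exposure. It leaves the first dose uncontrolled.

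Third, leaving urgent care to the treating staff is defensible. That also stands, and any added wording must respect it.

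Fourth, the earlier QTc data are reassuring. Section 10.6 reports all intervals below 450 msec in 42 women, and no clinical events consistent with cardiotoxicity. Only 13 of those women were on monthly DP (section 1.1). The median QTc change was 30 msec on monthly DP against 5 msec on 3-dose SP, a difference that was not significant. These data lower the alarm but do not address co-administration with a listed drug.

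Two stronger readings go too far. A reader might infer that ward staff have not been given the lists. The documents are silent on this, and briefings or site procedures may exist. A reader might also take clock time as a measure of risk: the clinic is open 9 hours a day, so 24 − 9 = 15 hours (15/24 = 62.5%) fall under 6.4. That is a share of hours, not of visits or prescriptions. The length of the lists says no more: 42 drugs in Appendix J plus 8 in Appendix K, less 2 on both, gives 48 entries, some of them marked as off the market.

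**Conclusion.** The concern holds in a limited form. Section 6.3 sets an avoid-and-consult safeguard; section 6.4 leaves after-hours non-malarial illness to hospital staff without stating that the safeguard carries over; and nothing in the protocol gives the ward the lists or a contact route. As written, the safeguard is not operational after hours, and existing steps act only after a first dose.

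This rests on the protocol text alone. If a ward briefing or site procedure already supplies the lists and a contact, the practical gap is closed and only the wording needs aligning. The number of women who would receive a listed drug cannot be computed, and the documents do not support a claim that such exposures will occur or be frequent. Randomization, endpoints, sample size and the primary analysis are unaffected. This is a cheap improvement for patient safety.

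**What to change.** Add to section 6.4:

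- The section 6.3 restriction on Appendix J and K drugs applies to enrolled pregnant women on study drugs, in either arm, when they are treated at the hospital after hours.
- The ward is given both lists, and listed drugs are avoided unless urgently required.
- Staff contact the clinical management team beforehand where feasible; otherwise the case is reviewed at the next-day clinic visit.
- Urgent care is not delayed for any of this.

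The cost is a few sentences of protocol text and copies of two existing lists; the next-day visit is already planned. The downside is one more list for ward staff to check. A new case report form item is not shown to be needed: the forms are not in the documents, and section 6.5 already asks about outside medications.

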6.5. Routine Assessments

Routine assessments will be done in the clinic every 4 weeks for both pregnant women and children. Study participants not seen in the clinic for their every 4 week routine visits will be visited at home and requested to come to the study clinic as soon as possible. Pregnant women and children will receive standards of care as designated in the Uganda MOH guidelines (Appendix F). Routine antenatal care will include screening and treatment for sexually transmitted Infections, blood pressure assessment, urine dipstick for proteinuria, prescription of iron, folate, multivitamins and mebendazole. Routine care in children will include immunizations, vitamin A supplementation, and management of anemia using Integrated Management of Childhood Illness (IMCI) guidelines. During routine assessments subjects will be asked about visits to outside health facilities and the use of any medications outside the study protocol. The study protocol will be reinforced with discussion regarding the need to come to the study clinic promptly upon the onset of any illness and to avoid use of outside medications. Standardized assessment of adherence will also be done for study drugs administered at home and ITN use. A routine history and physical exam will be performed using a standardized clinical assessment form. Blood will be collected by finger prick (in very young children, heel sticks may be substituted for finger pricks) for thick smear; capillary plasma, RDT testing, qPCR (for routine visits where phlebotomy is not done); and filter paper samples. In a subset of visits, less than 10 μ L of blood from finger prick or phlebotomy, if performed, will be used for magnetic levitation-based detection of malaria parasites. If a pregnant woman or parent/guardian of a child reports a fever in the last 24 hours or the patient has a documented temperature > 38.0°C tympanic, the patient's thick blood smear will be read immediately and if positive the patient will be diagnosed and treated for malaria (see section 6.2). In pregnant mothers, thick blood smears (other than those done when a mother has fever) and RDT testing will not be used for clinical care of study participants. Phlebotomy for routine laboratory tests (CBC and ALT) to monitor for potential adverse events from study medications, storage of plasma, RDT testing using PTS reader and experimental RDT, qPCR, and for immunology studies will be performed every 8 weeks in pregnant women. Phlebotomy for routine laboratory tests (hemoglobin measurement using a portable spectrophotometer (HemoCue Angholm, Sweden)), hemozoin based experimental rapid diagnostic test (experimentalMOD), standard RDT, microscopy, qPCR and immunology studies will be performed at 12, 28, and 52 weeks of age in children. For pregnant women, study drugs will be administered at the time of each routine visit as described in sections 5.3 and 5.4. ECGs will be performed to measure the QTc interval in all pregnant women just prior to the 1st dose of study drugs and 2-3 hours after their 3rd dose of study drugs at 20, 28 and 36 weeks of gestation. In addition a finger prick capillary plasma sample will be collected just prior to performing the ECGs after the 3rd dose of study drugs at 20, 28, and 36 weeks of gestation in pregnant women.

6.6. Delivery visit

Addressing one of the study outcomes, placenta malaria, requires collection and processing of specimens at delivery. Systems will be in place to facilitate a birth plan which will encourage women to come to the hospital for delivery, including access to transportation 24 hours a day. However for women who are unable to travel to the hospital for delivery or choose to deliver at home, a study staff member will be driven to the home to follow study procedures. Study staff will document details of the delivery, including date and time, type of delivery, estimated blood loss and any maternal, obstetrical or neonatal complications. Study staff will document the infant's Apgar score and birth weight with calibrated scales. Biological samples collected at the time of delivery will include maternal venous blood (for thick blood smear, filter paper samples, hemoglobin measurement, and immunology studies) and placental tissue. Following delivery, neonatal care, as per national guidelines, will include polio and BCG immunization, ophthalmic tetracycline, and vitamin K. On the day of birth newborns will have a heel stick or finger prick done for collection of blood for metabolic testing.

At the time of delivery, women will undergo repeat rapid HIV testing based on national guidelines. If women are found to have become HIV-infected during pregnancy, both the mother and their newborn will be withdrawn from the study and immediately referred for care following local prevention of mother-to-child transmission (PMTCT) guidelines.

6.7. Postpartum visits.

Women will be evaluated within 1 week following delivery and 6 weeks postpartum as part of routine care. Both visits will include an abdominal exam, syndromic management of STIs, and follow-up on any obstetrical complications that occurred including evaluation of the neonate for any congenital abnormalities. Pelvic and breast exam will be done if clinically indicated. Contraceptive counseling, nutritional assessment and infant feeding and support will be provided. Following the 6 weeks visit, women will no longer be considered study participants, although most will remain primary care givers for their children enrolled in the study.

Summaries of all procedures done during routine visits in pregnant women and children are presented in Appendix G and H, respectively.

6.8. Medical Care Outside the Study Clinic

We will provide routine medical care in our clinic free of charge, including medications, to the extent possible given resources available. Study participants and their guardians will be reimbursed for costs of any transportation to and from our clinic. In addition, we will

reimburse the cost of tests and drugs for referrals of study participants made by study physicians to other clinics and services as well as after-hours hospital visits. We anticipate reimbursing the cost of most diagnostic tests (including laboratory tests, X-rays, and ultrasounds) and medications resulting from these referrals, using available funds. However, reimbursement of all diagnostic tests and treatment recommended outside the study clinic cannot be guaranteed in all circumstances. Decisions on reimbursement will be made by the study coordinator and the investigators, in conjunction with the funding agency if necessary.

6.9. Duration of Follow-up and Criteria for Premature Study Withdrawal

Pregnant women will be followed until their 6 week postpartum visit. Children will be followed until they reach 12 months of age. Study participants will be prematurely withdrawn from the study for: 1) movement out of study area, 2) inability to be located for > 60 consecutive days, 3) withdrawal of informed consent, 4) inability to comply with the study schedule and procedures, 5) at the discretion of the site investigator if the study is not in the best interest of the participant, 6) subject or parent/guardian judged by the site investigator to be at significant risk of failing to comply with the study protocol as to cause them harm or seriously interfere with the validity of study results, 7) women found to have become HIV infected at the time of delivery (child withdrawal only). If a subject is withdrawn for reasons # 1-3, we will be unable to perform any additional study procedures. If a subject is withdrawn for reasons # 4-6, plans to obtain appropriate follow-up tests outside of the study will be individualized for each subject depending on the health status of the subject at the time of withdrawal and the willingness of the participant and his or her parent/guardian to proceed with additional testing. If a subject is withdrawn for #7, they will be referred for appropriate care following local PMTCT guidelines.

6.10. Diagnostic and Laboratory Testing

Diagnostic and laboratory testing shall take place using accredited local laboratories, as described below. In the event that local capacity is not available for specialized testing, reasonable efforts will be made to build local capacity. In the event that local capacity is not available, samples will be exported with all required permissions and permits to external testing laboratories. Table 2 lists examples of specialized testing, laboratories and rationale required to meet study aims.

Evaluation	Testing Laboratory	Rationale
Pharmacokinetic assessment of antimalarial drug levels	UCSF Drug Research Unit [name] University of California, San Francisco Department of Pharmacology	Measure piperaquine concentrations in venous specimens using liquid chromatography/ tandem mass spectrometry (LC/MS-MS). Testing equipment and expertise not available in-country.
Assessment of cord blood metabolites	Iowa State Hygienic Laboratory Ankeny, Iowa	Need for standardized mass spectrometry guidelines and referents
Immunologic studies of infants	Department of Pediatrics [name] University of California, San Francisco Division of Experimental Medicine	Testing equipment and expertise not available in-country for high- throughput immunologic assays, including RNA-sequencing

Table 2: Laboratory Evaluations Requiring Sample Export

6.10.1. Microscopy

Thick and thin blood smears will be stained with 2% Giemsa and read by experienced laboratory technologists. Parasite densities will be calculated by counting the number of asexual parasites per 200 leukocytes (or per 500 leukocytes, if the count is <10 asexual parasites/200 leukocytes), assuming a leukocyte count of $8,000/\mu$ l. A blood smear will be considered negative when the examination of 100 high power fields does not reveal asexual parasites. Gametocytemia will also be determined from thick smears. Thin smears will be used for parasite species identification. For quality control, all slides will be read by a second microscopist and a third reviewer will settle any discrepant readings.

